9.5.2 Exclusion of Time Points in Per Protocol Analysis

In the PP analysis of immunogenicity, samples with extensive time window deviations will be excluded from the analysis, even if the subject may remain in the PP analysis set. Any scheduled immunogenicity sample collected outside of the visit windows defined in the table below will be excluded from the PP analysis, but analyzed in the FAS.

Due to the fast onset of titer generation after immunization with VLA1553 and the long-term persistence of the titer without significant decrease over one year, the following protocol deviations related to time window deviations are classified as "minor protocol deviations" and do not exclude these subjects from the PP set (except for Visit 3 out of window as defined in section 9.4.3).

Table 9-2 Protocol deviation for immunogenicity samples collected outside of the visit window

Study Part	Visit	Study Day (Visit Window)
	Visit 0 (Screening)	Day -28 to 0 (prior to Visit 1)
	Visit 1	Day 1
	Visit 2	Day 8 (Week 1)
	Visit 3	Day 29 (Month 1)
	Visit 4	Day 85 (Month 3)
	Visit 5	Day 180 (Month 6)

10.0 Analyses Part A and Part B

10.1 Planned Analysis Timepoints

There are 2 planned data analyses on this study:

- Part A includes safety and immunogenicity data after all subjects have completed Visit 3 (Day 29).
- Part B includes safety and immunogenicity data after all subjects have completed Visit 5 (Month 6).

Individual study parts will be analyzed sequentially.

The study will be unblinded for Part A analysis once the final subject has completed Visit 3 and database lock for Part A has occurred (blind will be maintained for study sites and subjects). Unblinding of the study for Part B analysis will occur once the final subject has completed Visit 5 and database for Part B database has been locked.

The analyses to be done at each study part are specified within each section of the statistical methods part of this SAP.

For the Part A analysis, data up to and including Visit 3 (Day 29) or ET if earlier will be kept for all subjects, for the Part B analysis all data will be kept for all subjects. All AEs and concomitant medications with a start date up to and including the date of the cutoff visit for each subject will be included in the analysis. Any record with a start date prior to the cutoff which has a stop date recorded after the cutoff visit for the analysis will be classed as ongoing for the relevant study part.

11.0 Conventions and Derivations

11.1 Baseline and Change from Baseline

Unless otherwise specified, baseline will be defined as the latest assessment taken prior to the administration of the study drug. All procedures/assessments (apart from AE assessment) taken at Visit 1 are assumed to occur prior to vaccination.

Change from baseline is defined as:

Observed result at nominal time point – observed result at baseline.

11.2 Study Days and Visit Windows

Study day is defined relative to the day of vaccination (Visit 1). Study Day 1 is the day of vaccination (Visit 1). The scheduled study visits along with the predefined allowable visit window are included in the table below.

Table 11-1 Predefined visit windows

Study Part	Visit	Study Day (Visit Window)
	Visit 1	Day 1
	Visit 2	Day 8 (Week 1)
	Visit 3	Day 29 (Month 1)
	Visit 4	Day 85 (Month 3)
	Visit 5	Day 180 (Month 6)

Subjects who withdraw from the study prior to completion of the study will attend an Early Termination (ET) Visit where possible. For the purposes of analysis and reporting, each ET visit will be assigned to one of the two study parts. If the ET visit falls within the visit window for a scheduled visit then it will be summarized under that planned visit, unless a scheduled visit already exists within the time window. Otherwise, if a subject has an ET visit but no Visit 3 or later visits then the ET visit will be assigned to Part A, if the subject has an ET visit and a Visit 3 or later visit then the ET visit will be assigned to Part B.

Data will be analyzed according to the visit recorded on the CRF, except in the case of the immunogenicity analyses on the PP analysis set and ET visits. Unscheduled visits may be held at any time during the study as necessary, and may be included in the analyses of planned visits. Further, if an Unscheduled Visit falls into a Scheduled Visit window that either did not occur or occurred outside of the defined Scheduled Visit window, the Unscheduled Visit will be used in analyses in the place of the Scheduled Visit. Data at ET visits within the visit window for a scheduled visit will be summarized under the scheduled visit. Data at ET visits outside these visit windows will be listed only and may be included in summary tables. Similarly planned visits which fall into the window for a different planned visit will be analyzed according to the visit window they fall into rather than the recorded visit number. If there are multiple results falling into one visit after re-windowing, then a conservative approach will be taken, and the lower titer value will be used.

Analyses described as being presented at a study day will include all data up to the corresponding visit number. For example an analysis presented at Day 29 will include all data up to the subject's visit 3 timepoint, even if this is after study day 29. Similarly endpoints analyzed up to Day 180 will include all data collected on study, up to their Visit 5 or ET visit.

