6.1 Changes from Protocol

The Per Protocol analysis set uses different visit windows to define out of window results than outlined in the protocol schedule of events. This is in order to align the visit windows allowable in this analysis in line with the phase 1 study of this vaccine. The visit windows in the protocol are shown in section 11.2, whilst the windows for the exclusion from the Per Protocol analysis set are outlined in Section 9.5.2. Further, if an Unscheduled Visit falls into a Scheduled Visit window that either did not occur or occurred outside of the defined Scheduled Visit window, the Unscheduled Visit will be used in analyses in the place of the Scheduled Visit.

The definition of adverse event of special interest in section 11.7.5 has been updated per FDA feedback for clarification of the anatomical location with cutaneous pruritus. This is not yet reflected in Protocol version 3.0, which is the approved version at the time of SAP finalization.

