13.4 Immunogenicity Analyses

13.4.1 Hypothesis Testing Strategy and Multiplicity

A formal hypothesis test is defined for the primary immunogenicity analysis, using a two-sided significance level of 5%. There will be adjustment for multiplicity for primary immunogenicity endpoints if statistical significance (p-value ≤ 0.05 for any of the comparisons between the 3 Lots) is reached. To adjust for multiplicity in statistical comparison between the 3 Lots, the PDIFF=ANOM and ADJUST=NELSON option in PROC GLM will be used which analyzes all differences with the average least squares mean difference among the Lots. ANOM tests whether the treatment means differ from the overall mean (also called the grand mean); and if the least squares means are correlated, the ADJUST=NELSON option in PROC GLM

uses the factor-analytic covariance approximation described in Hsu (1992) for the underlying quantile calculation.

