13.4.2 Primary Immunogenicity Analysis

The primary immunogenicity analysis will be a comparison of the GMTs in the PP analysis set between the VLA1553 Lots 1, 2 and 3 at Day 29 (i.e. 28 days postvaccination) by ANOVA, using the factor Lot as a fixed effect and study center as a covariate. The ANOVA model will be applied to the log-transformed (natural log base e) μ PRNT values of the three Lots and the 95% CIs for the pair-wise ratios of the GMTs will be obtained by taking the anti-log of the resulting 95% CIs for the least square means differences. If these three pairwise 95% CIs for GMT ratios are all between [REDACTED] equivalence between the three commercial batches will be postulated.

The analysis will be performed on the PP analysis set and will be repeated on the Full analysis set.

For the PP analysis set there will be also produced the following graphical outputs:

- a line plot of the GMT at each study timepoint and treatment arm;
- a reverse cumulative distribution plot of the proportion of subjects by treatment arm.

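### SAP 11.2 calls keeping the lower of several in-window titers conservative; for the two-sided comparison between lots it is not, and a value-independent rule costs nothing

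*SAP*

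**What the plan says.** SAP 11.2 analyzes data under the visit recorded on the CRF, "except in the case of the immunogenicity analyses on the PP analysis set and ET visits". For those analyses samples are re-windowed: "planned visits which fall into the window for a different planned visit will be analyzed according to the visit window they fall into". When several results then share one visit, "then a conservative approach will be taken, and the lower titer value will be used". The rule does not distinguish one titer endpoint from another.

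The same section limits how multiples can arise. An unscheduled visit stands in for a scheduled one "if an Unscheduled Visit falls into a Scheduled Visit window that either did not occur or occurred outside of the defined Scheduled Visit window"; SAP 6.1 states the same substitution ("the Unscheduled Visit will be used in analyses in the place of the Scheduled Visit"). An early termination visit is placed under a planned visit "unless a scheduled visit already exists within the time window". The section also says, more loosely, that unscheduled visits may enter the analyses of planned visits, and it restates the early termination rule without that exception.

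SAP 9.4.3 makes the per-protocol (PP) set primary for immunogenicity. SAP 13.4.2 gives the primary criterion: "If these three pairwise 95% CIs for GMT ratios are all between" a lower and an upper limit (values redacted), equivalence of the lots is concluded.

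**The concern.** Choosing the lower titer makes the selected value depend on the outcome. That is cautious when the claim is that titers are high enough, as with a seroprotection rate in one group. The primary claim here is that three lots give similar GMTs. Lowering a lot that is truly equal to the others pushes it away from them; lowering a lot that is truly higher pulls it towards them. The first costs power and the second raises the chance of accepting lots that differ. The word conservative therefore gives no valid reason for the rule in this comparison. The visible text plans neither a sensitivity analysis with another selection rule nor a count of affected subjects per lot.

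**Working it through.** **Inputs from the documents.** 134 randomized per lot, allocation 1:1:1, SD 0.32 log10, overall power about 90%, losses of 10%, 5% and 2% (protocol 18.1, SAP 8.1); Day 29 window of ±4 days (protocol Table 15.4-1).

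**Assumptions.** The margin is redacted: 1.5 is used, with 1.45 and 2.0 as alternatives. The share of subjects with two titers in the window (f) and the SD between repeat titers (s) are not given: f from 2% to 20%, s from 0.10 to 0.32 log10. The value 0.32 equals the whole planning SD and is meant as a high end.

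**1. The plan's own figure.** Evaluable per lot: 134 × 0.83 = 111 with additive losses, or 134 × 0.90 × 0.95 × 0.98 = 112 with multiplicative ones. With a margin of 1.5 and truly equal lots, joint simulation of the three 95% CIs gives power of 91.5% (n = 111) and 92.0% (n = 112). A margin of 1.45 gives about 83% and 2.0 gives about 100%. A margin near 1.5 thus fits the stated 90%, but the documents do not allow this to be confirmed.

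**2. Shift per affected subject.** For two exchangeable normal titers, E[min] = mean − s/√π.
- s = 0.10: −0.056 log10, factor 0.878
- s = 0.20: −0.113 log10, factor 0.771
- s = 0.32: −0.181 log10, factor 0.660

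**3. Shift in a GMT ratio.** Between lots with affected shares f1 and f2, the log10 ratio moves by −(f1 − f2) × s/√π. Equal shares give zero.
- f1 = 5%, f2 = 0, s = 0.10: 0.05 × 0.0564 = 0.003 log10, factor 0.9935 (0.7% lower)
- f1 = 10%, f2 = 0, s = 0.20: 0.10 × 0.1128 = 0.011 log10, factor 0.974 (2.6% lower)

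For scale, the half-width of a pairwise 95% CI is about 1.967 × 0.32 × √(2/111) = 0.084 log10, so these shifts are 3% to 13% of it.

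**4. Both directions.** Margin 1.5 assumed, n = 112, only one lot affected. Each cell gives s = 0.15 / s = 0.32. For false acceptance, the affected lot is truly at the upper margin against one lot, with the third lot midway.

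| Share of one lot | GMT factor | Power, lots equal | False acceptance |
|---|---|---|---|
| 0% | 1.000 / 1.000 | 92.0% / 91.9% | 2.1% / 2.1% |
| 2% | 0.996 / 0.992 | 91.9% / 91.8% | 2.3% / 2.6% |
| 5% | 0.990 / 0.979 | 91.8% / 91.3% | 2.6% / 3.4% |
| 10% | 0.981 / 0.959 | 91.5% / 89.4% | 3.3% / 5.2% |
| 20% | 0.962 / 0.920 | 89.9% / 81.9% | 4.9% / 10.8% |

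With all three lots affected equally, power stayed between 91.8% and 92.0% at every share, so a change of 0.1 points is within simulation error. At 10% affected, a margin of 1.45 gives power of 82.4% / 79.7% (about 83% with no shift). A margin of 2.0 leaves power at 100% and gives false acceptance of 3.9% / 6.2% (2.5% with no shift).

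**5. How multiples could reach Day 29.** On the protocol's window (Days 25 to 33), Visit 2 would have to fall 17 or more days after its target, or Visit 4 at least 52 days before its own. The PP windows in SAP Table 9-2 differ from the protocol's and cannot be read here, so this is only a guide. What remains is mainly the looser wording on unscheduled and early termination visits.

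**The case against.** The strongest defense is that the rule hardly ever operates and treats all lots alike. Immunogenicity samples are planned only at the five scheduled visits, unscheduled visits substitute for a scheduled one rather than add to it, and early termination visits give way to a scheduled visit in the window. Lots are randomized and blinded, so nothing in the documents ties multiples to a lot. If they are independent of lot, the chance that all k affected subjects fall in a single lot is (1/3)^(k−1): 0.4% for 6 subjects (about 5% of 111) and under 0.002% for 11 (about 10%). The rule is also fixed before Part A unblinding and leaves the analyst no choice. All of this stands, and it is why the point is minor.

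Two further arguments stand in part. The primary analysis is repeated on the full analysis set, where planned visits keep their CRF label; but that set is also a different population, so the repeat does not isolate the rule. And the lower titer is indeed conservative for seroprotection and seroconversion rates within one group, so the rule need not be removed everywhere.

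None of this gives the lower titer a conservative direction in a two-sided comparison.

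**Conclusion.** The justification in SAP 11.2 is wrong for comparisons between lots, and the selection depends on the outcome. The expected effect on the primary conclusion is small: about 0.1 power points at 2% of one lot affected, and a GMT shift of 0.7% to 2.6% only in the extreme case of 5% to 10% of one lot and none of the others. These sizes rest on assumed repeat SDs and affected shares, and the power figures also on an assumed margin of 1.5.

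A reader might infer that the rule systematically biases the equivalence test. The documents do not support that: the rule is the same in every lot, allocation is randomized and blinded, and balanced multiples cancel in the ratio. The larger losses in the table need 10% to 20% of one lot affected, which nothing in the documents suggests. Nor is the substitution in SAP 6.1 an instance of choosing the minimum; it replaces one value with another and so limits multiples.

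**What to change.** In SAP 11.2, for the GMT and GMFI comparisons between lots, replace the lower-titer rule with one that ignores the titer value and is fixed before unblinding: the in-window sample closest to the target study day; on a tie, the scheduled visit's sample; then the earlier sample. For exchangeable titers this removes the selection bias entirely.

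Drop the description as conservative for these comparisons. The lower titer may stay for seroprotection and seroconversion rates within a single group. Leave several results on the same date and accession number to the existing record rule in SAP 11.5, so that the two rules do not collide. Report the number of subjects per lot with more than one in-window result.

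The cost is a short SAP edit and one added count. No new data, samples or subjects are needed, and the sample size does not change. It is a free improvement.

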11.3 Re-Screened Subjects

In this study subjects can be rescreened if they initially fail at screening and randomized into the study.

All available prior/concomitant medications and medical history will be re-entered into the latest applicable ID for a subject that is re-screened.

All other data will be mapped from the original ID to the latest applicable ID for a subject that is re-screened.

11.4 Handling of Duplicate Records

If there is duplicate entry of records into the system for any data then both records will appear in tabulation and analysis datasets and listings but only the first record will be flagged for use in the tables and figures.

11.5 Handling of Laboratory Records

If there are irreconcilable discrepancies between eCRF and vendor files in regards to differing visit label, visit date or accession number within a subject's results then subjects will be mapped by visit date and accession number.

[figure not shown]
The eCRF will be used as the ultimate source of data for these three variables. For frozen samples (including baseline samples, immunogenicity, and viremia samples), results will not be used from records where both visit date and accession number do not match. All other laboratory samples where a mismatch may occur between the ultimate source EDC data and vendor data, the samples will be reconciled and cleaned accordingly.

If there are multiple, non-duplicate records at the same visit date and accession number, then the worst case shall be used in tables and figures but all reported in listings. The worst case will be individual for each laboratory parameter and will be the lowest, highest or furthest from midpoint of normal range dependent on clinical relevancy. For example if there are two records of Calcium, as both high and low calcium is clinically relevant, the record furthest from the midpoint of normal range will be used.

Primary samples of baseline samples (all subjects), immunogenicity samples and selected Viremia Samples underwent sample reconciliation and cleaning – the eCRF is the ultimate source (except for irreconcilable items) for the associated back-up samples even in case of mismatches between visit date and accession number. For all other remaining samples where lab vendor records are mapped to EDC records, samples will be matched using Accession ID and date to reduce mismatches between the two records due to limitations in visit naming for the vendor samples.

11.6 Immunogenicity Endpoints

Immunogenicity assessment measuring neutralizing antibodies will be performed on samples collected at Days 1, 8, 29 (Month 1), 85 (Month 3) and 180 (Month 6) after a single immunization.

11.6.1 Geometric Mean Titer

The geometric mean titer (GMT) will be calculated as the anti-logarithm of the mean of the log-transformed titer. The geometric standard deviation (GSD) will be calculated as the anti-logarithm transformation of the standard deviation of the log-transformed titer. The 95% confidence interval (CI) will be calculated as the

anti-logarithm transformation of the upper and lower limits for a two-sided CI for the mean of the log-transformed titers.

11.6.2 Geometric Mean Fold Increase

The fold increase is calculated as the ratio of the post-vaccination titer value to the pre-vaccination value to determine the multiplicative increase from baseline result. Then, geometric mean is calculated as the anti-logarithm of the mean of the log-transformed values of (titer divided by the baseline assay result).

11.6.3 Seroconversion

Seroconversion is defined as a CHIKV-specific [REDACTED] for baseline μ PRNT negative subjects (PP, sPP1 for definition see section 9.4.3 and 9.4.4). Seroconversion for baseline μ PRNT positive subjects (included in PP) is defined as a [REDACTED] increase over baseline.

The seroconversion rate (SCR) is defined as the proportion of subjects meeting the criteria for seroconversion at the relevant study timepoint.

11.6.4 Seroprotection

Seroprotective levels of CHIKV-specific NT are defined as [REDACTED] at any post-baseline timepoint for baseline μ PRNT negative subjects.

The seroprotection rate (SPR) is defined as the proportion of baseline μ PRNT negative subjects meeting the criteria for seroprotection at the relevant study timepoint.

11.6.5 Fold-Increase in Neutralizing Antibody Titer

The fold-increase from baseline in the CHIKV-specific NT is defined as:

μ PRNT result at nominal time point / μ PRNT result at baseline.

The fold-increase will be summarized as a continuous endpoint. In addition, the number of subjects reaching pre-specified fold-increase categories of at least 4, 8, 16 and 64-fold increases compared to baseline will be summarized as the number and percentage of subjects in each category.

11.7 Adverse Events

An AE is defined as any untoward medical occurrence in a subject administered an investigational product that does not necessarily have a causal relationship with the treatment. All new abnormalities or any exacerbation in intensity or frequency (worsening) of a pre-existing condition during or after vaccination have to be documented as AEs.

Any untoward medical occurrence experienced before vaccine exposure (for example, from the time of signed informed consent up to but not including vaccine exposure) will not be considered an AE and will be described in the medical history.

A subject's death per se is not an event, but an outcome. The event which resulted in the subject's death must be fully documented and reported, regardless of being considered related to treatment or not.

Preexisting diseases that are described in the medical history, and that manifest with the same severity, frequency, or duration after vaccine exposure, will not be recorded as AEs. However, when there is an increase in the severity of a preexisting disease, the event will be recorded as an AE.

There is no definition of treatment-emergent in this study. Any AEs with an onset date prior to the date of vaccination will be raised with data management and should be moved to medical history.

All AEs entered on the CRF will be coded according to the Medical Dictionary for Regulatory Activities (MedDRA) Version 23.1 or higher. The following information will be documented on the CRF for each AE: severity, causality, outcome, seriousness, medically-attended, action taken to treat AE, start and stop dates.

11.7.1 Adverse Events Severity

All AEs will be assessed for severity by the Investigator using his/her clinical expertise. Severity will be categorized as Mild (Grade 1), Moderate (Grade 2) or Severe (Grade 3).

If the severity rating for an ongoing AE changes before the event resolves, the AE will not be reported a second time. Instead the original AE report will be revised. For purposes of data capture the highest severity rating during the course of a single AE will be the severity rating entered on the AE CRF. Any AE with missing severity will be classed as severe.

11.7.2 Causality

For AEs, the Investigator will assess the causal relationship between the IMP and the AE using his/her clinical expertise and judgement. Causality will be recorded as probable, possible, unlikely or not related.

AEs with a causality reported as probable or possible will be considered related to the IMP. AEs with missing causality assessment will be regarded as related unless further specified. All other AEs will be considered as not related to IMP.

